9.5.1 Analyses of Primary Efficacy Endpoint(s)

Not applicable

9.5.2 Analyses of Secondary Efficacy Endpoint(s)

The primary analysis of the incidence of a transfusion or hemoglobin \leq 8.0 g/dL from day 29 to EOETP will be based on the Cochran-Mantel-Haenszel method which will test for treatment group differences while adjusting for the stratification factors at randomization. In addition, the Mantel-

Haenszel estimate of the common odds ratio across strata will be estimated with a 95% confidence interval. This analysis will be performed on all subjects in the transfusion from week 5 to EOETP primary analysis set. If non-inferiority has been declared for OS and PFS, superiority will be declared for the transfusion endpoint if the p-value from a two-sided test of significance using the Cochran-Mantel-Haenszel method is less than 0.05 in favor of the darbepoetin alfa group.

The following sensitivity analyses will be performed:

- An analysis will be performed that removes the "hemoglobin ≤ 8.0 g/dL" from the definition of the endpoint in order to examine the treatment effect on the incidence of transfusion only from day 29 to EOETP.
- An analysis of transfusions when "hemoglobin ≤ 8.0 g/dL".
- To assess the impact of the early termination of the study, the analysis will be repeated for subjects who were still on-study or in long-term follow-up as of June 7 and for subjects who were not impacted by the early study termination.

9.5.3 Analyses of Exploratory Efficacy Endpoint(s)

An analysis similar to the analysis for transfusion or hemoglobin \leq 8.0 g/dL from week 5 to EOETP will be done for transfusion or hemoglobin \leq 8.0 g/dL from day 1 to EOETP (with a sensitivity analysis of incidence of a transfusion from day 1 to EOETP). These will be based on the Primary Analysis Set.

Descriptive statistics for change in hemoglobin from baseline will be provided at weeks 13 and 16 and graphs will be provided for hemoglobin over time (box plot) and change in hemoglobin from baseline over time (line plot) by treatment group. These will all be based on the Primary Analysis Set.

9.6 Safety Analyses

The following table summarizes the safety endpoints in this study, including the primary endpoint, overall survival, and the key secondary endpoint, progression-free survival.

Endpoint	Primary Summary and Analysis Method (Specify Analysis Set if FAS is Not Used)	Sensitivity Analysis	
Primary Safety Endpoint (primary endpoint of the study		()	
Overall Survival	Summarize the number of subjects with events and numbers of subjects censored, Kaplan-Meier quartiles, KM estimates of 1-year, 2-year, and 3-year	 Overall survival using: Full Analysis Set Overall survival using: Per- protocol Analysis Set 	

Table 9-1. Safety Endpoint Summary Table

	survival by treatment group. Present the hazard ratio with 95% confidence interval Dataset: Primary Analysis Set	•	KM time-to-event plots using the Primary Analysis Set, Full Analysis Set and Per-protocol Analysis Set Repeat analysis by stratification factors Dataset: Primary Analysis Set Repeat analysis for subjects impacted vs not impacted by early study termination Dataset: Primary Analysis Set Repeat analysis based on study day 1 rather than date of randomization Dataset: Full analysis set using targeted day 1 as the baseline use central laboratory hemoglobin values
Overall Survival	Cox proportional hazards regression modelling with treatment group in the model, stratified by the stratification factors. This will include the p-value testing for an interaction between treatment group and each stratification factor Dataset: Primary Analysis Set	•	Cox proportional hazards regression modelling including treatment group only. Dataset: Primary Analysis Set Cox proportional hazards regression modelling including the stratification factors and other clinically important covariates Dataset: Primary Analysis Set Results for stratification factors and covariates may be provided as a forest plot. Dataset: Primary Analysis Set
Overall Survival	Overall Survival with Adjustment for Cross-in using a Cox regression that estimates the hazard ratio with treatment group treated as a time- dependent covariate to account for cross-in of erythropoietic agent use by placebo Dataset: Primary Analysis Set		
Secondary	Safety Endpoint		
Progression- free Survival	Summarize the number of subjects with events and numbers of subjects censored, Kaplan-Meier quartiles, KM estimates of 1-year, 2-year, and 3-year survival by treatment group. Present the hazard ratio with 95% confidence interval Dataset: Radiographic Endpoint Primary Analysis Set	•	KM time-to-event plots using the Radiographic Endpoint Dataset: Radiographic Endpoint Primary Analysis Set Repeat analysis by stratification factors Dataset: Radiographic Endpoint Primary Analysis Set

		•	Repeat analysis using Radiographic Endpoint Full Analysis set Repeat analysis using Per Protocol Analysis set Repeat analysis for subjects impacted vs not impacted by early study termination Dataset: Radiographic Endpoint Primary Analysis Set
Progression- free Survival	Cox proportional hazards regression modelling with treatment group in the model, stratified by the stratification factors. This will include the p-value testing for an interaction between treatment group and each stratification factor Dataset: Radiographic Endpoint Primary Analysis Set	•	Cox proportional hazards regression modelling including treatment group only. Dataset: Radiographic Endpoint Primary Analysis Set Cox proportional hazards regression modelling including the stratification factors and other clinically important covariates Dataset: Radiographic Endpoint Primary Analysis Set
Progression- free Survival with Adjustment for Cross-in	Summarize the results of a Cox regression that estimates the hazard ratio with treatment group treated as a time-dependent covariate to account for cross-in of erythropoietic agent use by placebo Dataset: Radiographic Endpoint Primary Analysis Set		
Progression- free Survival to account for RECIST version	Summarize the results of a Cox regression that estimates the hazard ratio with treatment group treated and RECIST version as covariates Dataset: Radiographic Endpoint Primary Analysis Set		
Other Safety En	dpoint		
Time to disease progression	Summarize the number of subjects with events and numbers of subjects censored, Kaplan-Meier quartiles, KM estimates of 1-year, 2-year, and 3-year survival by treatment group. Present the hazard ratio with 95% confidence interval. Dataset: Radiographic Endpoint Primary Analysis Set	•	Repeat analysis by stratification factors Dataset: Radiographic Endpoint Primary Analysis Set KM time-to-event plots using the Radiographic Endpoint Dataset: Radiographic Endpoint Primary Analysis Set
Summary of Objective Tumor	Summarize the number and percent of subjects with an objective tumor response by treatment group; the	•	Repeat analysis stratified by RECIST version

Response Rate	difference in percent between treatment groups; the common odds ratio; and the Cochran-Mantel-Haenszel statistic and p-value Dataset: Radiographic Endpoint Primary Analysis Set		
Summary of Best Overall Objective Tumor Response	Summarize the number and percentage of subjects whose best overall response during the treatment period falls into each of the following categories: complete response, partial response, stable disease, disease progression, not evaluable, missing due to clinical progression, and missing for reasons other than clinical progression by treatment group Dataset: Radiographic Endpoint Primary Analysis set,	 Repeat analysis stratified by RECIST version Stratified by non-response to investigation product category Dataset: Safety Analysis Set 	
Product Dosing	and Medications		
Exposure to Investigational Product	Summarize the number and percent of subjects exposed to investigational product, and the dose and duration measures described.	•	Subgroup of subjects impacted or not impacted by early study termination
	Dataset: Safety Analysis Set		
Dose Changes to Investigational Product	Summarize the number and percent of subjects with dose reductions, dose withholdings, dose discontinuations, and switches to placebo for non- response	•	Subgroup of subjects impacted or not impacted by early study termination
 			
Summary of Concomitant Medications	rabulation of subjects receiving concomitant medication by WHODRUG preferred term by treatment group	•	Repeat for MOIs
	Dataset: Safety Analysis Set		
Summary of Treatment for NSCLC	Summarize the type and exposure NSCLC treatment by treatment group Dataset: Safety Analysis Set	•	Dataset: Primary Analysis Set
Summary of Erythropoiesis Stimulating Agents use Outside of	Summarize the amount of exposure to erythropoiesis stimulating agent use outside of investigational product by treatment group Dataset: Safety Analysis Set		
Product			
Adverse Events			
Overall Summary of Treatment- emergent	Tabulation of subjects experiencing the following types of summary of treatment-emergent adverse events: all, serious, those leading to withdrawal		

Adverse Events	of investigational product, and fatal by treatment group in the primary analysis set. Safety Analysis Set		
Treatment- emergent Adverse Events by SOC and Preferred	Tabulation of subjects experiencing any treatment-emergent adverse events by system organ class and preferred term in alphabetical order by treatment group Dataset: Safety Analysis Set	•	
Serious Treatment- emergent Adverse Events by SOC and Preferred Term	Tabulation of subjects experiencing serious treatment-emergent adverse events by system organ class and preferred term in alphabetical order by treatment group Dataset: Safety Analysis Set	•	Dataset: Primary Analysis Set
Summary of Treatment- emergent Adverse Events Leading to Withdrawal of Investigational Product by SOC and Preferred Term	Tabulation of subjects experiencing treatment-emergent adverse events leading to withdrawal of investigational product by system organ class and preferred term by treatment group in alphabetical order Dataset: Safety Analysis Set		
Summary of Fatal Treatment- emergent Adverse Events by SOC and Preferred Term	Tabulation of subjects experiencing fatal treatment-emergent adverse events by system organ class and preferred term by treatment group in alphabetical order Dataset: Safety Analysis Set		
Treatment- emergent Adverse Events of Interest by Category	Tabulation of subjects experiencing treatment-emergent adverse events of special interest by category (which include TVEs, VTEs and AEs associated with RBC transfusions) by treatment group in alphabetical order Dataset: Safety Analysis Set	•	Dataset: Primary Analysis Set
Treatment- emergent Serious	Tabulation of subjects experiencing treatment-emergent serious adverse events of special interest by category	•	Dataset: Primary Analysis Set

Adverse Events of Interest by Category	(which include TVEs, VTEs and AEs associated with RBC transfusions) by treatment group in alphabetical order Dataset: Safety Analysis Set		
Treatment- emergent Adverse Events of Interest by Category and Preferred Term	Tabulation of subjects experiencing treatment-emergent adverse events of special interest by category (which include TVEs, VTEs and AEs associated with RBC transfusions) and preferred term by treatment group in descending order of frequency Dataset: Safety Analysis Set		
Treatment- emergent Serious Adverse Events of Interest by Category and Preferred Term	Tabulation of subjects experiencing treatment-emergent adverse events of special interest by category (which include TVEs, VTEs and AEs associated with RBC transfusions) and preferred term by treatment group in alphabetical order Dataset: Safety Analysis Set		
Treatment emergent VTEs	VTEs confirmed and not confirmed by imaging, including fatal and non- fatal VTEs. Subjects with or without a history of VTE will also be included	•	Dataset: Primary Analysis Set
	Datasot: Safoty Analysis Sot		
Treatment emergent Serious VTEs	Dataset: Safety Analysis Set Serious VTEs confirmed and not confirmed by imaging, including fatal and non-fatal VTEs. Subjects with or without a history of VTE will also be included Dataset: Safety Analysis Set	•	Dataset: Primary Analysis Set
Treatment emergent Serious VTEs Serious VTEs Treatment- emergent Adverse Events Occurring in ≥ 5% of All Subjects in Descending Order of Frequency	Dataset: Safety Analysis Set Serious VTEs confirmed and not confirmed by imaging, including fatal and non-fatal VTEs. Subjects with or without a history of VTE will also be included Dataset: Safety Analysis Set Tabulation of subjects experiencing any treatment-emergent adverse events by treatment group in descending order of frequency in the total column and coded by preferred term Dataset: Safety Analysis Set	•	Dataset: Primary Analysis Set

Order of Frequency		
Treatment- emergent Adverse Events in Descending Order of Frequency by SOC, Preferred Term and Grade	Tabulation of subjects experiencing any treatment-emergent adverse events by treatment group in descending order of frequency and coded by preferred term and grade Dataset: Safety Analysis Set	
Treatment- emergent Serious Adverse Events in Descending Order of Frequency by SOC, Preferred Term and Grade	Tabulation of subjects experiencing any treatment-emergent adverse events by treatment group in descending order of frequency and coded by preferred term and grade Dataset: Safety Analysis Set	
Laboratory Resu	ults	
Clinical Laboratory	Summary statistics for baseline, minimum on study, maximum on study, EOTP, and change from baseline to EOTP by treatment group will be provided for: Hemoglobin Platelets White blood cell count Serum ferritin Serum iron Transferrin saturation level (TSAT) Total iron binding capacity Creatinine Total bilirubin Alanine aminotransferase (ALT), and Aspartate aminotransferase (AST) 	N/A Note: data for all other analytes will be provided in an electronic format
Summary of Hemoglobin	Summarize the number and percent of subjects who had hemoglobin > 12.0	

Threshold – Primary Analysis Set	g/dL at any time in the treatment period (both adjusting and not adjusting for RBC transfusions) by treatment group Dataset: Safety Analysis Set	
Summary of Rapid Rate of Rise in Hemoglobin – Primary Analysis Set	Summarize the number and percent of subjects who had a rapid rate of rise in hemoglobin (> 1.5 g/dL in 21 days) at any time in the treatment period (both adjusting and not adjusting for RBC transfusions) by treatment group Dataset: Safety Analysis Set	
Summary of Non-response to Investigational Product – Primary Analysis Set	Summarize the number and percent of subjects who were non-responders by treatment group Dataset: Safety Analysis Set	
Antibody Result	s, Vital Signs, ECOG	
Summary of Antibody Results –	Summarize antibody results for darbepoetin alfa by treatment group Dataset: Safety Analysis Set	 Summarize antibody results for erythropoetin by treatment group Dataset: Safety Analysis Set
Summary of Vital Signs	Summarize weight, systolic blood pressure, diastolic blood pressure, pulse by treatment group Dataset: Safety Analysis Set	
Summary of ECOG Performance Status	Summarize ECOG by treatment group Dataset: Safety Analysis Set	

9.6.1 Primary Safety Endpoints

The primary analysis of OS will be based on the primary analysis set and will use a Cox regression model, stratified by the randomization factors, with treatment group as the only covariate. Subjects last known to be alive will be censored on date of last contact. Non-inferiority will be declared if the upper confidence limit for the hazard ratio (darbepoetin alfa to placebo) is less than 1.15 using a 1-sided significance level of 0.025.

The following sensitivity analyses will be performed as further exploratory analyses for the primary endpoint:

- To provide a completely unadjusted analysis, a hazard ratio with 95% confidence interval will be estimated from an unstratified Cox regression with treatment group as the only covariate.
- To support the results obtained from the primary analysis set, analyses will be performed using the overall survival per protocol set.
- To explore the consistency of the treatment effect, Cox regression models will be generated including the stratification variables and covariates listed in Section 4.1. These models will include any interaction terms with treatment group where nominal p-values of <0.10.
- In addition, a hazard ratio with 95% confidence interval will be generated from an unstratified Cox regression for each stratum formed from the combination of randomization factors (e.g., subjects from North America with squamous cell and who have a screening hemoglobin < 10.0 g/dL) and for each level of a given stratification factor (e.g., subjects from North America).
- To explore the impact of cross-in (placebo subjects who begin erythropoiesis stimulating agents at any point after randomization), an analysis will be performed that models erythropoiesis stimulating agent use as a time-dependent covariate in the stratified Cox regression. For subjects randomized to the darbepoetin alfa arm, the time-dependent covariate will be coded "1" throughout the time course (with the exception of subjects randomized to darbepoetin alfa who mistakenly receive placebo; they will be coded "0" throughout the time course unless they begin use of any erythropoiesis stimulating agent). For subjects randomized to the placebo arm, the time-dependent covariate will initially be coded "0" and change to "1" if and when they begin use of any erythropoiesis stimulating agent. Because the time-dependent covariate is based on information post-randomization, the results of this analysis will be interpreted with caution.
- To assess the impact of misspecifications of the stratification factors at randomization, a hazard ratio with 95% confidence interval will be estimated from an unstratified Cox regression with treatment group as a covariate along with covariates that represent the stratification factors. The values of the stratification factors will be determined from the case report forms rather than the IVRS. This analysis will only be done if there is evidence that there were errors in the IVRS stratification factors.
- To assess the impact of the early termination of the study, the primary analysis will be repeated for subjects who were still on-study or in long-term follow-up

as of June 7 and for subjects who were not impacted by the early study termination.

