10.6.2 Analysis of Key Study Endpoints

10.6.2.1 Analysis of Primary Endpoint

The analysis of OS will use a Cox proportional hazards model, stratified by the randomization factors, with treatment group as the only covariate (a sensitivity analysis will include additional covariates described in Section 10.2.3 to assess the robustness of the primary approach). Subjects last known to be alive will be censored on date of last

contact. Non-inferiority will be declared if the upper confidence limit for the hazard ratio is less than 1.15 using a 1-sided significance level of 0.025.

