4.1 Planned Covariates

- Stratification factors:
 - Geographic region (some regions may be combined for analysis):
 - Region 1: Belgium, Germany, Israel, Italy, Luxembourg, Netherlands, Spain, Switzerland, South Africa, UK
 - Region 2: Bulgaria, Czech Republic, Greece, Poland, Romania, Russia, Serbia, Slovenia, Ukraine
 - Region 3: Argentina, Brazil, Chile, Hong Kong, South Korea, Malaysia, Mexico, Philippines, Taiwan
 - Region 4: India
 - Region 5: Canada, United States (reference group)
 - Region 6: China
 - Region 7: Japan (analyzed as part of Region 3)
 - Histology: Squamous vs non-squamous cell (reference group)
 - Screening hemoglobin level: <10 g/dL vs >=10 g/dL (reference group)
- Potentially clinically important covariates:
 - NSCLC platinum-based chemotherapy vs. other chemotherapy (reference group)
 - NSCLC Targeted therapy (anti-EGFr or anti-angiogenic agents or other) vs. none (reference group)
 - o Baseline serum erythropoietin: ≤100 mU/mL vs >100 mU/mL (reference group)
 - History of VTEs: yes vs. no (reference group)

Note that the reference group will be coded a "0" in any statistical modeling including stratification factors and/or covariates.

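### Does keeping treatment interactions with p<0.10 in the exploratory covariate Cox models put the covariate-adjusted hazard ratio at risk?

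*SAP*

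**What the plan says.** Protocol 10.6.2.1 makes the primary analysis of overall survival (OS) a Cox model stratified by the randomisation factors, with treatment as the only covariate. It adds a sensitivity analysis that "will include additional covariates described in Section 10.2.3 to assess the robustness of the primary approach". Protocol 10.2.3 lists factors that additional analyses may include. Neither section mentions interactions.

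The SAP takes up covariates in two places.

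- **SAP 9.6.1, sensitivity bullets.** "To explore the consistency of the treatment effect, Cox regression models will be generated", containing the stratification variables and the Section 4.1 covariates. The next sentence is "These models will include any interaction terms with treatment group where nominal p-values of <0.10". The following bullet gives separate hazard ratios (HRs) by stratum and "for each level of a given stratification factor". The whole list is introduced as exploratory.
- **SAP 9.6, safety endpoint summary table, OS Cox row.** The method cell holds the stratified primary model and says "This will include the p-value testing for an interaction between treatment group and each stratification factor". The sensitivity cell lists "Cox proportional hazards regression modelling including the stratification factors and other clinically important covariates", without interaction terms. The progression-free survival (PFS) row has the same entry on its own analysis set: "Cox proportional hazards regression modelling including the stratification factors and other clinically important covariates Dataset: Radiographic Endpoint Primary Analysis Set".

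SAP 4.1 codes the reference group as 0 "in any statistical modeling including stratification factors and/or covariates". SAP 9.6.2 says the PFS sensitivity analyses will be similar to those for OS. The SAP does not say whether the 9.6.1 bullet and the table entry are one model or two.

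**The concern.** The protocol's covariate analysis is meant to show whether the primary HR is robust, which calls for a comparable adjusted HR. If the 9.6.1 bullet is the only covariate model, the data decide what its treatment coefficient means. Once an interaction enters and the reference level is coded 0, that coefficient is the log HR at the reference level of the factor. It rests on fewer deaths, and the factor was selected because its levels appeared to differ.

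Reported as the adjusted HR, it could contradict a sound primary result by chance, or look reassuring when the overall HR sits at the margin. The rule would act often, and SAP Section 10 does not list it as a change from the protocol. PFS would inherit the same treatment through 9.6.2.

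**Working it through.** **Inputs from the documents.** Protocol 10.3: 2700 deaths, margin 1.15, one-sided 0.025, true HR 1.0, power about 93%. Protocol 10.1: 2:1 allocation. SAP 4.1: three stratification factors and four other covariates, with Japan analysed in Region 3, which leaves six regions. SAP 3.2: the study ended with 2549 subjects.

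**1. The plan's own figure.** The variance of the log HR is V = 1/(2700 × 2/3 × 1/3) = 1/600, so SE = 0.0408. Power = Φ(ln 1.15/0.0408 − 1.96) = Φ(3.42 − 1.96) = Φ(1.46) = 92.8%. The stated 93% is reproduced.

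**2. How often the rule would act.** With no true interaction and independent tests, P(at least one kept) = 1 − 0.9^k.

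| Tests | k | P(at least one kept) |
|---|---|---|
| Stratification factors only | 3 | 27% |
| Four other covariates only | 4 | 34% |
| All seven factors | 7 | 52% |
| Single terms (5 for region + 2 + 4) | 11 | 69% |

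A simulation of 400 trials with assumed covariate frequencies gave 53% for seven factors and 68% for eleven terms.

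**3. What a kept interaction does to the coefficient.** Take one binary factor whose reference level holds a share f of the deaths. The SE at that level is √(V/f). Given that the interaction was kept, the reference-level log HR equals the overall log HR minus √(V(1−f)/f) × Z, with |Z| > 1.645. At f = 0.5 the displacement is at least 1.645 × 0.0408 = 0.067 in either direction. At f = 0.9 it is at least 1.645 × 0.0136 = 0.022. The documents give no shares, so f is an assumed range.

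| f | SE | P(upper limit <1.15 given kept), true HR 1.0 | Same, true HR 1.15 |
|---|---|---|---|
| No interaction in the model | 0.041 | 93% | 2.5% |
| 0.9 | 0.043 | 86% | 4% |
| 0.7 | 0.049 | 69% | 8% |
| 0.5 | 0.058 | 54% | 13% |
| 0.3 | 0.075 | 50% | 17% |

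Averaged over all trials with seven factors, using the main-effects fit when nothing is kept, the chance at true HR 1.0 is 0.522 × 86% + 0.478 × 93% = 89% for f = 0.9, and 0.522 × 54% + 0.478 × 93% = 73% for f = 0.5.

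**4. Whether these rates describe a decision in the plan.** They do not. The requirement that the upper limit lie below 1.15 applies to the primary model, which contains no covariate and no interaction. The covariate models have no pass criterion. The death count is also superseded: 2700 deaths cannot occur among 2549 subjects. The table shows only how badly a reference-level coefficient would stand in for an overall HR if someone used it that way.

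**5. What is lost if the levels are reported properly.** Nothing. The two level-specific log HRs have variances V/f and V/(1−f). Weighted by f and 1−f they return the overall estimate, with variance f²(V/f) + (1−f)²(V/(1−f)) = V. The overall effect is hidden only if one level is shown alone.

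**6. The two SAP places side by side.** The table entry is a covariate model for OS with no interactions. The 9.6.1 bullet speaks of models in the plural and gives consistency of effect as its purpose, for which keeping notable interactions is a natural choice. Interaction tests for the stratification factors already have their own place in the method cell of the same table row, and level-specific HRs for those factors are the next bullet in 9.6.1. Read together, the main-effects adjusted model is the table entry and the interaction models are a further exploration.

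**The case for a change.** The best case for a change is that the SAP never links the table entry to the bullet. If they are the same model, the operative text is the mandatory p<0.10 rule, and two programmers could produce different numbers for the protocol's robustness analysis. No other planned analysis plainly fills that place. The primary and unadjusted models carry no covariates, and the model using case report form values adjusts for stratification factors only and runs only if there were randomisation-system errors. After early termination the supportive analyses will be read more closely, and one sentence would settle the matter at no cost.

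Some of this stands. The link is not stated, the rule is data-driven, and the four covariates outside the stratification factors have no interaction test of their own. But it would be wrong to call the table row silent on interactions, since its method cell asks for them by stratification factor; only the covariate entry omits them. The protocol does not promise an overall covariate-adjusted HR in so many words; that is inferred from its aim of checking robustness. The damage also needs a further step that no document calls for: reporting a reference-level coefficient as though it were overall. An analyst who keeps an interaction will know that the treatment coefficient now refers to one level, and will show the levels.

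**Conclusion.** No change to the plan is needed. The gap is real but small: the SAP leaves unsaid which of two exploratory covariate models answers the protocol's robustness question. The plain reading supplies the answer, because the table entry is a main-effects adjusted model and the 9.6.1 models examine consistency.

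The primary non-inferiority decision, the margin, the alpha and the order of testing do not depend on either model, so following the SAP as written leaves the conclusion sound. An added sentence would mainly record which model is reported.

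The 52% retention figure assumes seven independent tests and no true heterogeneity. The SE range of 0.043 to 0.075 assumes one binary factor, one kept interaction, reference shares of 90% to 30%, and the planned 2700 deaths. The judgement would differ only if the SAP directed that the treatment coefficient from a model with a kept interaction be presented as the overall adjusted HR, and it does not.
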